Subject Population:	The subjects will be male or female, between 18 and 65 years of age (inclusive) at the time of Screening, with a body mass index (BMI) between 18 and 35 kg/m ² (inclusive) at the time of Screening. The subjects will have an estimated glomerular filtration rate (eGFR) \geq 60 mL/min/1.73 m ² (Cohort 1 and 3), or eGFR \geq 30 to < 60 mL/min/1.73 m ² (Cohort 2 and 4), with eGFR calculated by the Chronic Kidney Disease Epidemiology Collaboration (CKD-EPI) equation. Subjects will have been diagnosed with ADPKD based on modified Ravine criteria.
Study Design:	This is a Phase 2, open-label, parallel-group, multiple dose study designed to evaluate the PK, PD, safety, and tolerability of multiple BID doses of 50 and 200 mg lixivaptan in ADPKD subjects with chronic kidney disease in stages CKD1, CKD2 or CKD3.

Estimated Study Duration:	
Screening Duration: 42 days (Day -44 through Day -3)
 
Confinement Period: Subjects will be confined from Check in (Day -2 or Day-1) until Day 2 in the morning. Subjects will be confined from Day 6 in the afternoon through Day 8 in the morning.
 
Outpatient: Subjects will return to the clinical research unit (CRU) on an outpatient basis on Day 4 in the morning and Day 6 in the morning for a trough PK assessment.
 
End of Study Visit: Subjects will return on Day 35 (± 2) for end of study assessment.
 
Total Study Duration: Up to 80 days
																				

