3.1.1 Rationale of Study Design

The I/E criteria in Section [4.1](#) were chosen to recruit an adequate number of subjects representative of the ADPKD population to achieve the study's primary objectives as presented in Section [2.1.1](#).

Based on existing clinical evidence with lixivaptan and the related vasopressin antagonist tolvaptan, the PK and PD properties of lixivaptan are not expected to differ in ADPKD subjects with CKD1 and CKD2 stages, therefore these subjects with relatively preserved kidney function will be combined into one study group. This approach decreases the total number of subjects that need to be recruited without compromising the study objectives. Conversely, subjects with moderately impaired renal function (CKD3 stage) may show distinct PK and PD responses to lixivaptan and will be enrolled into a separate group.

The PK profile of lixivaptan and its metabolites will be monitored for 3-5 half-lives after the last dose to define terminal PK parameters. Therefore, PK blood draws are included up to 96 hours, i.e. approximately 4 half-lives of the longest-lived metabolite of lixivaptan, after the last dose of lixivaptan (Day 7 PM).

Treatment with lixivaptan is associated with transient and reversible increases in serum creatinine and circulating vasopressin. In addition, based on clinical evidence with the related vasopressin antagonist tolvaptan,¹² lixivaptan may be associated with transient and reversible decreases in Total Kidney Volume (TKV). In order to characterize the time course and magnitude of these pharmacodynamic effects of lixivaptan in ADPKD subjects, the study design includes measurements of serum creatinine, plasma copeptin as a marker for circulating vasopressin, and TKV at three time points: at baseline, after completion of the scheduled treatment period and 4 weeks after the last dose of lixivaptan.

The sample size of 32 subjects in total, with 16 subjects per Cohort, is typical for this type of study and is considered adequate to meet the study objectives.

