5.3 Treatments Administered

Subjects assigned to one of the 2 dose levels of lixivaptan (Table 5-1) will receive oral lixivaptan BID (AM and PM) from Day 1 through Day 7. The PM dose will be administered approximately 10 hours after the AM dose.

Table 5-1 Study Cohorts and Lixivaptan Dose Levels

Cohort	CKD stage	Dose*	N	
1	CKD1 or CKD2	200 mg BID	8 subjects	Candidate maximum tolerated dose
2	CKD3	200 mg BID	8 subjects	
3	CKD1 or CKD2	50 mg BID	8 subjects	Candidate lowest effective dose
4	CKD3	50 mg BID	8 subjects	

*PM dose to be administered approximately 10 hours after the AM dose

Prior to the morning doses on Days 1 and 7, subjects will fast overnight for ≥ 8 hours prior to study medication administration. Water will be allowed *ad libitum* during the overnight fasting. Liquids (other than water) are considered part of the ≥ 8 hour overnight fast.

In the morning of Days 1 and 7, subjects will receive lixivaptan with room temperature water (approximately 240 mL [8 ounces]) and will remain fasted for 2 hours after dosing. Water

will be allowed *ad libitum* during the 2 hours fasting, however subjects will be required to abstain from consuming other liquids until 2 hours after dosing.

The evening doses on Days 1 and 7 will be administered in the CRU under fasting conditions, i.e. 2 hours before and 2 hours after meals. Liquids (other than water) are considered part of the 2 hour fast.

Study drug will be administered orally to subjects. Administration of each dose of study drug while the subject is confined at the CRU will be supervised, verified, and documented according to the CRU's standard operating procedures. A mouth and hand check will be performed immediately after study drug administration.

The actual date and time of each dose administration will be entered in the eCRF.

When not confined to the CRU, subjects will self-administer lixivaptan with water (approximately 240 mL) and without fasting. Subjects will continue to adhere to the recommended fluid intake regimen outlined in [Section 5.9](#).

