6.1.9 Adverse Events

6.1.9.1 Definitions of Adverse Events

The Investigator is responsible for reporting all AEs that are observed or reported during the study, regardless of their relationship to study drug or their clinical significance, as outlined in [Section 6.1.9.2](#) below.

An AE is defined as any untoward medical occurrence in a subject enrolled into this study regardless of its causal relationship to study drug.

A treatment-emergent AE (TEAE) is defined as any event not present before exposure to study drug or any event already present that worsens in either intensity or frequency after exposure to study drug.

An SAE is defined as any event that results in death, is immediately life threatening, requires in-subject hospitalization or prolongation of existing hospitalization, results in persistent or significant disability/incapacity, or is a congenital anomaly/birth defect. Important medical events that may not result in death, be life threatening, or require hospitalization may be considered SAEs when, based upon appropriate medical judgment, they may jeopardize the subject or may require medical or surgical intervention to prevent one of the outcomes listed in this definition.

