6.1.9.2 Eliciting and Documenting Adverse Events and Serious Adverse Events

AEs and SAEs that are related to study participation (e.g., protocol-mandated intervention) will be recorded from the time the subject signs the ICF until the start of study treatment. All other AEs and SAEs will be recorded from the start of study treatment until exit from the study. Other changes in health or new symptoms occurring during the screening period will be recorded as medical history.

At every study visit, subjects will be asked a standard nonleading question to elicit any medically related changes in their well-being. They will also be asked if they have been hospitalized, had any accidents, used any new medications, or changed concomitant medication regimens (both prescription and over-the-counter medications).

In addition to subject observations, AEs will be documented from any data collected that is deemed clinically significant by the Investigator (e.g., laboratory values, physical examination findings, vital signs, or ECG changes) or identified from review of other documents (e.g., subject diaries) that are relevant to subject safety.

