### 16.1. ADVERSE EVENTS

Adverse events (AEs) will be coded using the most recent version of MedDRA.

Treatment emergent adverse events (TEAEs) are defined as any event not present before exposure to study drug and subsequently started, or any event already present that worsens in either intensity or frequency, after exposure to study drug. An algorithm for determining whether AE is treatment-emergent if AE start date or AE end date is unknown is described in Appendix 2.

Any AEs and serious adverse events (SAEs) related to study participation (e.g., protocol-mandated intervention) will be recorded from the time the subject signs the informed consent form until the start of study treatment. All other AEs and SAEs will be recorded from

Document: \liedc-vnasc01\BIOSdata\Palladio\Lixivaptan\WYA34000\Biostatistics\Documentation\SAP\PA102 SAP V1.0 NonPKPD 25APR2019

Author: [name] Version Number:

Version Date: 1.0

Version Date: 25 April 2019

Template No: CS\_TP\_BS016 – Revision 5 Reference: CS\_WI\_BS005

Effective Date: 01Apr2018

Palladio Biosciences STATISTICAL ANALYSIS PLAN: PROTOCOL PA-102 Page 23 of 36

the start of study treatment until exit from the study.

Any abnormal laboratory test results (hematology, clinical chemistry, or urinalysis) or other safety assessments (e.g., ECGs, vital sign measurements), including those that worsen from baseline, deemed to be clinically significant in the medical and scientific judgment of the investigator are to be recorded as AEs or SAEs. Any safety assessments that are associated with the underlying disease, unless judged by the investigator to be more severe than expected for the subject's condition, are not to be reported as AEs or SAEs.

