### **ALGORITHM FOR TREATMENT EMERGENCE OF ADVERSE EVENTS:**

START DATE	STOP	ACTION
	DATE	
Known	Known	If start date < study med start date, then not
		TEAE
		If start date >= study med start date, then TEAE
	Partial	If start date < study med start date, then not
		TEAE
		If start date >= study med start date, then TEAE
	Missing	If start date < study med start date, then not
		TEAE
		If start date >= study med start date, then TEAE
Partial, but known	Known	Not TEAE
components show that		

 ${\tt Document:} \qquad {\tt \underline{\label{losdata}Palladio}\label{losdata} Palladio} \\ {\tt \underline{\label{losdata}}\label{losdata} Palladio} \\ {\tt \underline{\label{losdata}}\label{losdata} Palladio} \\ {\tt \underline{\label{losdata}}\label{losdata} Palladio} \\ {\tt \underline{\label{losdata}}\label{losdata}\label{losdata} Palladio} \\ {\tt \underline{\label{losdata}}\label{losdata}\label{losdata}\label{losdata} Palladio} \\ {\tt \underline{\label{losdata}}\label{losdata}\label{losdata}\label{losdata}\label{losdata}\label{losdata}\label{losdata} Palladio \\ {\tt \underline{\label{losdata}}\label{losdata}\label{losdata}\label{losdata}\label{losdata}\label{losdata}\label{losdata}\label{losdata}\label{losdata}\label{losdata}\label{losdata}\label{losdata}\label{losdata} Palladio \\ {\tt \underline{\label{losdata}}\label{losdata}\l$ 

102 SAP V1.0 NonPKPD 25APR2019

Author: [name] Version Number: 1.0

Version Date: 25 April 2019

Template No: CS\_TP\_BS016 - Revision 5 Reference: CS\_WI\_BS005

Effective Date: 01Apr2018

Palladio Biosciences STATISTICAL ANALYSIS PLAN: PROTOCOL PA-102 Page 36 of 36

START DATE	STOP	ACTION
	DATE	
it cannot be on or after		
study med start date		
	Partial	Not TEAE
	Missing	Not TEAE
Partial, could be on or	Known	If stop date < study med start date, then not
after study med start		TEAE
date		If stop date >= study med start date, then TEAE
	Partial	Assumed TEAE
	Missing	Assumed TEAE
Missing	Known	If stop date < study med start date, then not
		TEAE
		If stop date >= study med start date, then TEAE
	Partial	Assumed TEAE
	Missing	Assumed TEAE

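### The treatment-emergent AE window has a start but no end, so the safety tables pool a 7-day course and its 96-hour washout with about 24 further days off drug and show no split by onset

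*SAP*

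**What the plan says.** Three places define a treatment-emergent event (TEAE), and all look only at the start of exposure.

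- Protocol 6.1.9.1: "A treatment-emergent AE (TEAE) is defined as any event not present before exposure to study drug", or an existing event that worsens.
- Non-PK/PD SAP 16.1: "Treatment emergent adverse events (TEAEs) are defined as any event not present before exposure to study drug and subsequently started", again with worsening added.
- Non-PK/PD SAP Appendix 2, for a known onset date: "If start date >= study med start date, then TEAE".

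On duration, subjects "will receive oral lixivaptan BID (AM and PM) from Day 1 through Day 7" (protocol 5.3). Adverse events are gathered for much longer: "All other AEs and SAEs will be recorded from the start of study treatment until exit from the study" (protocol 6.1.9.2). For completers that exit is set in the synopsis: "Subjects will return on Day 35 (± 2) for end of study assessment".

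SAP 16.1.2 tabulates TEAEs per cohort by SOC/PT, by severity and by relationship, giving subjects, percentages and event counts. When a subject has the same SOC/PT term more than once, the worst severity (16.1.1) and the worst relationship (16.1.2) are reported. The SAP text describes no table divided by time of onset.

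**The concern.** Safety and tolerability is a primary objective and the SAP's primary estimand (7.2). The study is open-label with no untreated arm, so no table shows what background events would look like. In that setting, timing relative to exposure is one of the main ways to tell a drug effect from an intercurrent event, and the tables drop it.

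Two consequences follow. First, unrelated events in the off-drug weeks count in the same rows as events on drug and can raise the reported incidence. Second, the worst-case rules run across the whole window. As a constructed example, a subject with a mild headache on Day 2 and a severe one on Day 25 appears once, as severe. The relationship table only partly corrects for this, because SAP 16.1.2 treats unknown or missing causality as possibly related.

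The SAP uses end-of-treatment logic elsewhere: laboratory shifts run to the last on-treatment observation (16.3), and concomitant medications are defined by the treatment period (12).

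**Working it through.** **The plan's own AE figure.** Protocol Table 7-1 gives the chance of seeing no case of an event among 8 subjects. The formula is (1 − p)^8. For p = 0.1, 0.2, 0.3, 0.4 and 0.5 it gives 0.4305, 0.1678, 0.0576, 0.0168 and 0.0039, which matches the stated 0.43, 0.168, 0.058, 0.017 and 0.004. The documents state no off-drug share and no background rate.

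**Inputs for the window.** Last dose: Day 7 PM (protocol 5.3). Exit: Day 35 ± 2 (synopsis). Residual exposure: protocol 3.1.1 says "PK blood draws are included up to 96 hours, i.e. approximately 4 half-lives of the longest-lived metabolite of lixivaptan", counted from the last dose, which takes the exposed period to Day 11 (7 + 4). After 4 half-lives, 0.5^4 = 6.25% of that metabolite remains, so Day 11 is an approximate boundary.

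**Share of a completer's counted time that is off drug** = (exit day − last exposed day) / exit day.

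| Exit day | Exposed to Day 11 (96 h added) | Exposed to Day 7 (dosing days only) |
|---|---|---|
| 33 | 22/33 = 66.7% | 26/33 = 78.8% |
| 35 | 24/35 = 68.6% | 28/35 = 80.0% |
| 37 | 26/37 = 70.3% | 30/37 = 81.1% |

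In hours from first dose, the last dose falls at 6 × 24 + 10 = 154 h and the morning of Day 35 at 34 × 24 = 816 h. The share is (816 − 154 − 96)/816 = 69.4%.

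**Effect of one subject on a row.** 1/8 = 12.5 percentage points per cohort.

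**Illustration of inflation (assumed rates, not in the documents).** With a constant rate r, the chance that a subject has at least one background event of any kind in t days is 1 − exp(−rt).

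| Assumed rate | 11 days | 35 days |
|---|---|---|
| 1 per 120 person-days | 9% | 25% |
| 1 per 60 person-days | 17% | 44% |
| 1 per 30 person-days | 31% | 69% |

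For a single event type with an assumed 10% incidence over 35 days, incidence in 11 days is 1 − 0.9^(11/35) = 3.3%. The chance of at least one case in a cohort of 8 is then 1 − 0.9^8 = 0.57 with the open window and 1 − (1 − 0.0326)^8 = 0.23 with a Day 11 cut. At an assumed 5% the pair is 0.34 and 0.12; at 20% it is 0.83 and 0.43.

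**The case against.** The open window has reasons behind it. The SAP repeats the protocol definition. Its estimand counts subjects whether or not they stop early, although it sets no time window. The protocol follows reversibility to 4 weeks after the last dose (3.1.1), and it cites serious liver injury with a related drug (1.3). Collecting events to Day 35 is sound, and the total should stay.

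Two stronger readings are tempting, and the documents do not support them.

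- A reader might infer that follow-up events dilute the early aquaretic signal. They cannot. The percentages are of subjects, not of person-time, so extra follow-up can only add subjects to a row.
- A reader might infer that investigator causality is the only remaining filter. It is not. Study day appears in every listing with an event date (SAP 6.2), and AE listings give start and end times. The tolerability questionnaire is taken on Days 2 and 7 and summarized separately (SAP 16.7), and laboratory values and vital signs are summarized by timepoint (SAP 16.3, 16.5). With about 32 subjects, a reader can recover onset from the listings by hand.

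The illustrative rates also assume even capture, which the schedule does not provide. The diary records events only through the week after the last dose (protocol 5.7.1), and Table 12-1 has no visit between Day 11 and Day 35. The 35-day figures are therefore probably an upper view. Finally, the SAP leaves table layout to templates that are not reproduced in it, so an onset display there cannot be excluded, though the text mentions none.

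These points limit the consequence and its size. They do not supply the missing split in the summary tables.

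**Conclusion.** The point holds as a gap in presentation. No end limit exists in the protocol definition, the SAP text or the algorithm. For a completer, 69% of the counted window lies beyond the 96-hour washout (67% to 70% across the exit window), or 80% by dosing days alone. The first figure rests on the protocol's approximate half-life statement. Both apply to subjects followed to about Day 35; for early terminators the share is smaller, and percentages mix unequal observation times.

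Background events in follow-up can raise TEAE incidence and can set the worst-case severity or relationship of a term first seen on drug. How much they will do so cannot be derived from the documents, and any background rate is an assumption. No data are lost and the analysis is recoverable, but the tables that report a primary objective should show the split without recourse to listings.

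**What to change.** Keep the TEAE definition and its total. In Non-PK/PD SAP 16.1 and Appendix 2, add a flag by onset:

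- **On-treatment:** first dose through 96 hours after the last dose actually taken.
- **Post-treatment:** later, to study exit.

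Show both columns and the total in the SOC/PT, severity and relationship tables. Apply the worst-case rules within each period and overall. Appendix 2 allows partial AE dates, so a rule is needed for them: a partial or missing onset that could fall in the on-treatment period goes to on-treatment, in line with the algorithm's present practice of assuming emergence when dates are uncertain. Footnote early terminators whose follow-up is cut short, possibly before the 96 hours have passed.

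The cost is one derived flag, its partial-date rule and extra table columns. No new data are needed and the listings do not change. The downside is that late drug effects will sit in the post-treatment column. So will laboratory abnormalities first detected at Day 35, since Table 12-1 schedules no clinical laboratory tests between Day 8 and Day 35. Both columns and the total must therefore be read together.

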Changes from baseline in vital signs at each scheduled timepoint will be summarized by renal function group for the Safety Analysis Set using descriptive statistics (n, mean, SD, median, minimum, and maximum). The baseline value is defined as the last value observed prior to first administration of study drug. The change from baseline is defined as the post-baseline value minus the baseline value. There will not be any imputation for missing values. All vital sign data will be listed individually by each subject based on the Safety Analysis Set.

Physical Examinations

Changes in baseline in physical examination findings (Normal, Abnormal-NCS, Abnormal-CS) will be summarized using counts and percentages for renal function group and will also be listed individually for each scheduled timepoint.

Adverse Events

An overall summary of the number and percentage of subjects in each category will be presented, as will an overall summary of the number of events in each category. The number and percentage of subjects reporting AEs in each category above will be summarized by renal function group according to the system organ class (SOC) and preferred term (PT) assigned to the event using MedDRA.

All AE data will be listed for all subjects. Both the Investigator's verbatim terms and the MedDRA preferred terms will be listed for each subject. Listings will also include the SAEs, start and end time and date of AEs, relationship to study drug, severity, and action taken for the AEs. A summary of deaths (for all deaths, AE outcome, not AE term, is death) will be provided by number and percentage of subjects by renal function group.

Questionnaire for Tolerability

Tolerability data obtained from the questionnaire will be listed and summarized as detailed in the SAP.

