### 6.2. REFERENCE START DATE AND STUDY DAY

Study day will be calculated from the reference start date and will be used to show the start/stop day of assessments and events.

Document: \\ieedc-vnasc01\BIOSdata\Palladio\Lixivaptan\WYA34000\Biostatistics\Documentation\SAP\PA-

4 102 SAP V1.0 NonPKPD 25APR2019
Author: [name]

Version Number: 1.0

Version Date: 25 April 2019

Template No: CS\_TP\_BS016 – Revision 5 Reference: CS\_WI\_BS005

Effective Date: 01Apr2018

Palladio Biosciences STATISTICAL ANALYSIS PLAN: PROTOCOL PA-102

Page 13 of 36

The reference start date is defined as the day of the first dose of study medication (Day 1 is the day of the first dose of study medication). Study day will be calculated relative to reference start date and will appear in every listing where an assessment date or event date appears.

If the date of the event is on or after the reference date, then:

Study Day = (date of event - reference date) + 1.

If the date of the event is prior to the reference date, then:

Study Day = (date of event – reference date).

If the event date is partial or missing, the study day and any corresponding durations will be missing in the listings.

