#### 6.3. **BASELINE**

Unless otherwise specified, baseline is defined as the last non-missing measurement taken prior to reference start date (including unscheduled assessments). In the case where the last non-missing measurement and the reference start date coincide, that measurement will be considered pre-baseline, but Adverse Events (AEs) and medications commencing on the reference start date will be considered post-baseline.

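### The date-only TEAE rule counts a study-procedure event that starts on Day 1 before the first dose as treatment-emergent, against the plan's own exposure-based definition

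*SAP*

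**What the plan says.** **Definition.** Protocol 6.1.9.1 gives the TEAE definition (its closing word, drug, is left off here): "any event not present before exposure to study drug or any event already present that worsens in either intensity or frequency after exposure to study". Non-PK/PD SAP 16.1 keeps the same idea, "any event not present before exposure to study drug and subsequently started", together with the worsening limb. Both definitions turn on exposure, not on the calendar day.

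**Rule.** The Appendix 2 algorithm, wherever the start date is known, reads "If start date >= study med start date, then TEAE". SAP 6.3 agrees with it: "Adverse Events (AEs) and medications commencing on the reference start date will be considered post-baseline". SAP 6.2 makes that reference a day and not a date-time: "The reference start date is defined as the day of the first dose of study medication".

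**What is recorded before dosing.** Under protocol 6.1.9.2, events related to study participation are recorded from consent until treatment starts. Other new symptoms in the screening period go to medical history.

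**Times available.** Protocol 6.1.9.3 collects the time of AE onset. Protocol 7.7.3 and SAP 16.1.2 plan listings with "start and end time and date of AEs". Protocol 5.3 has the actual date and time of each dose entered in the eCRF.

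**The concern.** The operational rule does not implement the definition on the one day when both predose procedures and the first dose take place. An event that demonstrably began before any exposure would be flagged treatment-emergent, and the recorded times that show the true order would not be used.

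Safety and tolerability is a primary objective, and TEAEs are tabulated by cohort with 8 subjects planned in each, so a single misplaced subject is visible in a percentage. SAP 3.3 declares no meaningful change from the protocol, so nothing tells a reader that the tables depart from the protocol definition for Day 1 events.

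**Working it through.** The plan states no figure that depends on this rule, so there is nothing to reproduce. The check has four parts.

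**1. Can such an event arise?** Before the Day 1 morning dose the subject fasts overnight for at least 8 hours (protocol 5.3). The 0-hour PK sample is drawn (Table 12-1, footnote 13) up to 60 minutes before the dose (Table 12-2). An ECG is taken (footnote 7), and blood pressure and pulse are measured (footnote 8). A participation-related event from any of these is recordable under protocol 6.1.9.2.

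**2. Do the two rules differ?** Take an illustrative first dose at 08:00 on Day 1. Apply the date rule (onset date on or after dose date) and a date-time rule (onset date-time at or after dose date-time) to four onsets:

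| Onset | Date rule (Appendix 2) | Date-time rule |
|---|---|---|
| Day -1, 18:00 | not TEAE | not TEAE |
| Day 1, 07:15 | TEAE | not TEAE |
| Day 1, 09:00 | TEAE | TEAE |
| Day 2 | TEAE | TEAE |

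Only the predose onset on Day 1 changes class. For that onset, the date-time rule gives the answer that the definition requires.

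**3. Where would it be counted?** SAP 16.1.2 tabulates TEAEs by cohort by SOC and PT, by SOC, PT and severity, and by SOC, PT and relationship. The event enters the first two whatever its causality. In the third it would normally fall in the not-related row, because protocol Table 6-2 assigns that category where there has been no exposure to the product.

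**4. Size per subject.** If the affected subject has no other event of that term:

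- cohort: 1/8 = 12.5 percentage points
- all subjects: 1/32 = 3.1 percentage points

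The documents give no rate q for such events. Purely as an assumption, the chance of at least one affected subject among n is 1 − (1 − q)^n:

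| Assumed q | n = 8 | n = 32 |
|---|---|---|
| 1% | 7.7% | 27.5% |
| 2% | 14.9% | 47.6% |
| 5% | 33.7% | 80.6% |
| 10% | 57.0% | 96.6% |

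This range shows sensitivity to q and is not evidence that such events are common.

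**The case against.** **The rule is stated and conservative.** SAP 6.3 settles the same-day tie expressly, the two places agree, and the error is toward over-counting, so no drug-related event is hidden. All of that is true. It does not remove the conflict with the definition in SAP 16.1, which carries no Day 1 exception.

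**Scope.** SAP 16.1 introduces Appendix 2 as the algorithm for unknown dates, and the appendix is titled as a partial-date convention, so the text definition arguably governs fully dated events. This does not succeed. Appendix 2 has its own row for known start and known stop dates, and SAP 6.3 states the convention independently.

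**Causality.** Investigators assess every event, and a predose event should be coded not related. The listings show both onset time and relationship. This stands: a reader might infer that counts of drug-related events are inflated, and the documents do not support that. The exception would be an event with missing or unknown causality, which SAP 16.1.2 handles as possibly related.

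**Narrowness.** Only participation-related events with onset between midnight and the morning dose are exposed. A bruise first noted after dosing is a TEAE under either rule. If the same term recurs after dosing, the term's incidence does not change, and ten further PK draws are scheduled that day. This also stands.

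**No decision depends on it.** Safety summaries are descriptive, without between-group tests (SAP 16). This stands and limits the importance of the point.

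**Conclusion.** The inconsistency is real, and it is confined to study-participation events with known onset on Day 1 before the first dose. For those events Appendix 2 and SAP 6.3 give the opposite answer to protocol 6.1.9.1 and SAP 16.1, and the data needed to decide correctly are collected. What is affected is the all-causality SOC/PT and severity tables. The size is 12.5 points per affected subject in a cohort of 8, provided that 8 subjects are treated and the subject has no other event of that term.

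A reader might infer that the TEAE incidences are materially distorted. The documents do not support this: they give no frequency for such events, and the exposed class is small. A reader might also count Day 1 safety laboratory draws among the sources. Table 12-1 marks them on Day 1 but the laboratory row of Table 12-2 omits that day, so the point rests on the fast, the PK draw and the ECG instead. This is a worthwhile tidying of the plan, not a threat to its conclusions.

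**What to change.** Change Appendix 2 and the AE clause of SAP 6.3 together:

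- When the AE start date equals the first-dose date and onset time is known, compare onset date-time with first-dose date-time. Onset at or after the dose is a TEAE. Onset before the dose is not, unless the event worsens in intensity or frequency after dosing.
- When onset time is missing, keep the present date rule.

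The worsening clause has to be written out, because Appendix 2 as it stands has no branch for an event that begins before dosing and then worsens.

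The cost is SAP wording in two places and about one line of code. No new data are needed, and no event with postdose or unknown onset time changes class.
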